### 3.3.4 Removal of subjects from therapy or assessments

#### 3.3.4.1 Removal of individual subjects

An individual subject is to be removed from the trial if:

1. The subject withdraws consent for trial treatment or trial participation, without the need to justify the decision
2. The subject needs to take concomitant drugs that interfere with the investigational product or other trial medication
3. The subject is no longer able to participate for other medical reasons (such as surgery, adverse events, or diseases)
4. An AE or clinically significant laboratory change or abnormality occurred that the investigator judges to warrant discontinuation of treatment. This may include cases of sustained symptomatic hypotension (BP <90/50 mmHg) or hypertension (BP >180/100 mmHg) or of clinically relevant changes in ECG requiring intervention as well as unexplained liver enzyme elevations at any time during the trial.
5. The subject shows an elevation of AST and/or ALT  $\geq 3$ -fold ULN combined with an elevation of total bilirubin  $\geq 2$ -fold ULN (measured in the same blood sample) and/or needs to be followed up according to [Appendix 10.1](#) of this clinical trial protocol and the 'DILI checklist' provided in the ISF.

In addition to these criteria, the physician may discontinue subjects at any time based on his or her clinical judgment.

Infusion reactions should also lead to the removal of an individual subject. However, in mild transient cases of infusion reactions (with clinical symptoms such as dizziness, headache, nausea) requiring no treatment the clinical investigator may pause the infusion or continue with a reduced infusion rate as described for other therapeutic proteins [\[P16-06636\]](#).

However, the overall infusion time (including time of discontinuation) must not exceed 45 minutes for 3 mg/kg b.w. and 6 mg/kg b.w. multiple dose and 90 minutes for 10 mg/kg b.w. multiple dose and 20 mg/kg b.w. single dose and 120 minutes for 20 mg/kg b.w. multiple dose.

A subject can also be removed from the trial if eligibility criteria are being violated or if the subject fails to comply with the protocol (for instance, by non-adherence to dietary rules, or non-attendance at study assessments).

If a subject is removed from or withdraws from the trial prior to first administration of trial medication, the data of this subject will not be entered in the case report form (CRF) or trial database and will not be reported in the clinical trial report (CTR). If a subject is removed from or withdraws from the trial after first administration of trial medication, this will be documented and the reason for discontinuation must be recorded in the CRF. In this case, the data will be included in the CRF/trial database and will be reported in the CTR. At the time of discontinuation a complete end of trial examination will be performed if possible and the information will be recorded in the CRFs. If the discontinuation occurs before the end of the REP (see [Section 5.2.2.2](#)), the discontinued subject should if possible be questioned for AEs and concomitant therapies at or after the end of the REP in order to ascertain collection of

AEs and concomitant therapies throughout the REP, if not contrary to any consent withdrawal of the subject. These discontinuations will be discussed in the CTR.

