#### 4.1.4 Drug assignment and administration of doses for each subject

The treatments to be evaluated are outlined in [Table 4.1.4: 1](#) below. The dose volume for placebo corresponds to the dose volume of the respective dose level. For further details concerning timing see [Flow Chart](#). Start and time of the infusion will be recorded.

Detailed instructions for the dilution of the trial product, the preparation of the infusion solution, the volume to be administered and the infusion rate is provided in [Appendix 10.2](#). In all subjects the infusion solution will be intravenously administered over 30 minutes for dose group 3 mg/kg b.w. multiple dose and 6 mg/kg b.w. multiple dose and over 60 minutes for dose group 10 mg/kg b.w. multiple dose and 20 mg/kg b.w. single dose approximately between 8.00 h and 10.30 h of the respective study day. Multiple doses of 20 mg/kg b.w. will be administered over 90 minutes between 8.00 h and 12.00 h of the respective study day.

In case of safety concerns, e.g. due to infusion reactions, it is in the discretion of the investigator or his/her designee to adapt the infusion scheme, including but not limited slowing down the infusion rate, stopping of the infusion and provided no further safety concern exist restarting at a slower rate. Further based on █ medical judgment he/she will provide medications such as steroids, etc. as needed.

For administration of the infusion, an intravenous indwelling catheter is placed into an arm vein of the subject and will be kept patent with a saline infusion. A second indwelling catheter used for collection of blood samples will be placed on the contralateral arm.

The administration of the trial medication on all study days will be done under supervision of the investigating physician or a designee. The so-called four-eye principle (two-person rule)

should be applied for administration of trial medication and – if applicable – its preparation (e.g. reconstitution), if correct dosage cannot be ensured otherwise. For the purpose of drug accountability, the infusion set will be weighed before and after drug administration.

Table 4.1.4: 1 Preparation of infusion solution containing active drug

Dose group	Final dose of BI 655130 [mg/kg]	Concentration of Application solution in infusion bag	Infusion volume [mL]*/ Total dose [mg]
1	3	20 mg/mL	9 mL → 180 mg
2	6	20 mg/mL	18 mL → 360 mg
3	10	20 mg/mL	30 mL → 600 mg
4	20	20 mg/mL	60 mL → 1200 mg
5	20	20 mg/mL	60 mL → 1200 mg

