## 7.6 DETERMINATION OF SAMPLE SIZE

It is planned to include a total of 40 subjects in this trial. The planned sample size is not based on a power calculation. The size of 8 subjects per dose group (6 on active treatment, and 2 on placebo) is considered as sufficient for the exploratory evaluation of multiple dose safety and pharmacokinetics [[R95-0013](#)].

Additional subjects may be entered to allow testing of intermediate doses within the planned and approved dose range on the basis of experience gained during trial conduct (e.g. preliminary PK data), i.e. the actual number of subjects entered may exceed 40.

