**Infusion Information:**

Dose (mg/kg)	In-line Filter Used?	Approximate Pre-flush Volume (mL)	Concentration of the ready to use i.v. bag BI 655130 (mg/mL)	Volume Delivered (mL/kg body weight)	Infusion Time (min)
3	Yes	30	5	0.6	Up to 240
6	Yes	15	10	0.6	Up to 240
10	Yes	15	20	0.5	Up to 240
20	Yes	15	20	1	Up to 240

After preparation, the solution for infusion may be stored at 2-8°C for up to 24 hours. After removal from 2-8°C storage or preparation, the solution must be administered within 60 minutes if stored at  $\leq 25^{\circ}\text{C}$ . Do not freeze.

Chemical and physical in-use stability has been demonstrated for 60 minutes at  $\leq 25^{\circ}\text{C}$ . In addition the time for infusion must not exceed 240 minutes at  $\leq 25^{\circ}\text{C}$ .

From a microbiological point of view the drug should be used immediately. If not used immediately, the in-use storage times and conditions prior to use are the responsibility of the user, and would normally not be longer than 24 hours at 2-8°C (36-46°F), unless preparation has taken place in controlled and validated aseptic conditions.

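### Protocol Sections 3.3.4.1 and 4.1.4 give different rules for an infusion reaction that needs treatment or is not mild and transient

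*Protocol*

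**What the plan says.** Protocol Section 3.3.4.1 lists the reasons for removing a subject from the trial and then adds a rule on infusion reactions: "Infusion reactions should also lead to the removal of an individual subject". It makes one exception. In mild and transient cases "requiring no treatment the clinical investigator may pause the infusion or continue with a reduced infusion rate". The following paragraph limits the total duration: "the overall infusion time (including time of discontinuation) must not exceed 45 minutes for 3 mg/kg b.w. and 6 mg/kg b.w. multiple dose". The same sentence gives 90 minutes for 10 mg/kg multiple dose and 20 mg/kg single dose, and 120 minutes for 20 mg/kg multiple dose.

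Protocol Section 4.1.4 gives planned durations of 30 minutes (3 and 6 mg/kg multiple dose), 60 minutes (10 mg/kg multiple dose, 20 mg/kg single dose) and 90 minutes (20 mg/kg multiple dose). For safety concerns, "e.g. due to infusion reactions, it is in the discretion of the investigator or his/her designee to adapt the infusion scheme". The options it lists include slowing the infusion and "stopping of the infusion and provided no further safety concern exist restarting at a slower rate". A separate sentence lets the investigator give medication as needed, with steroids as the example. For the infusion rate the section refers to Appendix 10.2.

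The infusion table in Appendix 10.2 shows up to 240 minutes for each of the four doses. The text below it says "In addition the time for infusion must not exceed 240 minutes" at 25 °C or less, beside the in-use stability statements.

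Protocol Section 3.1 puts a check of the Section 3.3.4.1 stopping criteria into the minimum data set for each escalation review. It also requires at least six evaluable subjects per dose level before escalation.

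**The concern.** Sections 3.3.4.1 and 4.1.4 both instruct the investigator about the same event. Take a reaction that is treated with medication and then settles. It falls outside the exception in Section 3.3.4.1, so that section points to removal. Under Section 4.1.4 the investigator may restart the infusion once no further safety concern exists. Two investigators could act differently and each cite the protocol.

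The first thing at stake is re-exposure: whether a subject who reacted receives the rest of that infusion. In the multiple-dose groups up to three weekly infusions may still be scheduled (Days 8, 15 and 22 after a reaction on Day 1).

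The second is the escalation review. A subject restarted under Section 4.1.4 would appear there as someone who met a removal rule that was not applied. The choice can also affect how many subjects count as evaluable.

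Duration raises a smaller question. Someone who adapts an infusion under Section 4.1.4 and follows its reference for the rate finds only the 240-minute figure in Appendix 10.2, not the caps in Section 3.3.4.1.

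**Working it through.** The plan has no figure to reproduce. Section 7.6 says "The planned sample size is not based on a power calculation", and no frequency of infusion reactions is given. The check is therefore a comparison of the texts, with simple arithmetic on the stated counts and times.

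**Step 1: apply both sections to the same event.**

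| Reaction | Section 3.3.4.1 | Section 4.1.4 | Same answer? |
|---|---|---|---|
| Mild, transient, no treatment needed | Pause or slow permitted | Slow, stop or conditional restart permitted | Compatible |
| Needs treatment, then settles | Outside the exception: removal is the default | Conditional restart permitted; medication permitted | No |
| Not mild and transient, no treatment given, then settles | Outside the exception: removal is the default | Conditional restart permitted | No |

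The divergence is confined to the second and third rows.

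**Step 2: look for a rule of precedence.** Section 4.1.4 states no severity limit and does not mention Section 3.3.4.1. Section 3.3.4.1 does not mention Section 4.1.4. Nothing in the available text says which governs.

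**Step 3: escalation condition.** Inputs from Section 3.1: 6 active + 2 placebo = 8 subjects per group, and at least 6 evaluable subjects per dose level. The available text does not define evaluable, so the effect of a removal is a range:
- If only active subjects count and a removed subject is not evaluable: 6 − 1 = 5, below 6 after a single removal.
- If all eight count and a removed subject is not evaluable: 8 − 2 = 6 still meets the condition; 8 − 3 = 5 does not.
- If a removed subject stays evaluable, the count does not change.

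Replacement could restore the count, but Section 3.3.5 leaves it to a case-by-case decision.

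**Step 4: are the time limits compatible?**

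| Dose group | Planned (4.1.4) | Cap (3.3.4.1) | Appendix 10.2 | Durations where only the cap is exceeded |
|---|---|---|---|---|
| 3 and 6 mg/kg multiple dose | 30 min | 45 min | up to 240 min | above 45, up to 240 min |
| 10 mg/kg multiple dose, 20 mg/kg single dose | 60 min | 90 min | up to 240 min | above 90, up to 240 min |
| 20 mg/kg multiple dose | 90 min | 120 min | up to 240 min | above 120, up to 240 min |

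Since 45, 90 and 120 are all below 240, any infusion that respects its cap also respects the 240-minute limit. The limits can be met together. What is missing is a statement of what the 240 minutes are for and a pointer to the caps.

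**The case against.** The strongest reply is that Section 3.3.4.1 states a default and Section 4.1.4 a permission, so they are not opposite instructions. The first says should, not must. The second does not direct a restart, and makes one conditional on there being no further safety concern. Medication is a separate sentence, not tied to restarting, so treating a subject and then removing him satisfies both sections. Section 4.1.4 also concerns the infusion in progress and says nothing about later weekly doses.

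Most of this is correct and limits the point. It does not remove it. Section 3.3.4.1 defines one exception, and a treated reaction lies outside it. A discretion to restart with no severity limit covers cases that the default assigns to removal. Exposure at later visits is an inference: it follows only if a restarted subject stays on the weekly schedule.

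On duration, the defence largely succeeds. A reader might infer that 240 minutes contradicts the 45-, 90- and 120-minute caps. The documents do not support that. The figure is the same for all doses, carries a temperature condition and stands beside the stability text. The amendment log attributes the infusion-time update in the reconstitution instructions to an in-use stability study. Section 4.1.4 states the planned durations itself. What remains is an unlabelled figure reached through a cross-reference.

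Section 2.3 is not in the available text, and the amendment log lists it among the sections that carried the change in infusion time. It may explain how these rules fit together.

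**Conclusion.** The point holds in a limited form. For an infusion reaction that needs treatment, or that is not mild and transient, Section 3.3.4.1 points to removal and Section 4.1.4 permits a conditional restart, with no rule of precedence. The consequences are possible re-exposure of a subject who reacted, an unclear reading of the stopping-criteria check, and an uncertain evaluable count at escalation. How often this would arise cannot be estimated, because the documents give no reaction rate. The time limits are a secondary ambiguity.

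Two stronger conclusions are tempting and should not be drawn:
- A reader might infer that the primary result depends on which section is followed. It does not: the endpoint is the number of subjects with drug-related adverse events, and a drug-related reaction counts whether or not the subject is removed.
- A reader might infer that the count of other significant adverse events would shift. SAP Section 7.8.1 puts discontinuation and reduction in the same class, and adds events leading to significant concomitant therapy. Moving an event between discontinuation and reduction does not change that count. A discontinuation rate is not a defined endpoint.

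The conclusion assumes that should in Section 3.3.4.1 is meant as a default, and that Section 2.3 does not already reconcile the two sections.

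**What to change.** Reconcile Sections 3.3.4.1 and 4.1.4 so that one rule applies to the same infusion reaction, and have each section refer to the other. In Appendix 10.2, state the purpose of the 240-minute figure and how it relates to the dose-group caps in Section 3.3.4.1. Which clinical rule and which limits apply is for the sponsor to decide; this review takes no position.

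The cost is protocol wording only. No procedure, visit, sample or analysis is added.

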### 3.3.4.2 Discontinuation of the trial by the sponsor

Boehringer Ingelheim reserves the right to discontinue the trial overall or at a particular trial site at any time for any of the following reasons:

1. New toxicological findings or serious adverse events invalidate the earlier positive benefit-risk-assessment. More specifically, the trial will be terminated if more than 50% of the subjects show drug-related and clinically relevant adverse events of moderate or severe intensity, or if at least one drug-related serious adverse event is reported that is considered to be unacceptable.
2. The expected enrolment goals overall or at a particular trial site are not met
3. Violation of GCP, or the CTP, or the contract with BI by a trial site or investigator, disturbing the appropriate conduct of the trial
4. The sponsor decides to discontinue the further development of the investigational product.
5. Dose escalation will be stopped as soon as at least 2 subjects at one dose level on active drug showed relevant individual QT prolongation, i.e. a QTc increase of greater 60 ms from baseline in connection with absolute QT or QTc greater than 500 ms, which has been confirmed by a repeat ECG recording.

The investigator / the trial site will be reimbursed for reasonable expenses incurred in case of trial termination (except in case of the third reason).

### 3.3.5 Replacement of subjects

In case some subjects do not complete the trial, the trial clinical monitor together with the trial pharmacokineticist and the trial statistician are to decide if and how many subjects will be replaced. A replacement subject will be assigned a unique study subject number, and will be assigned to the same treatment as the subject █ replaces.

## 4. TREATMENTS

### 4.1 TREATMENTS TO BE ADMINISTERED

The investigational product has been manufactured by BI Pharma GmbH & Co. KG. The BI 655130 molecule is a heterodimer with a molecular weight of approximately 146 kDa.

#### 4.1.1 Identity of BI investigational product and comparator product

The characteristics of the test product are given below:

Substance: BI 655130

Pharmaceutical formulation: solution for infusion

Source: BI Pharma GmbH & Co. KG, Germany

Unit strength: 150 mg/7.5 mL (per 10 mL vial)

Posology: 1-0-0

Route of administration: IV infusion

Duration of use: Single dose (20 mg/kg b.w.)

Multiple dose (4 single IV administrations one week apart)

At the time of use, the IV solution for dosing will be prepared as detailed in the instruction given in [Appendix 10.2](#).

The characteristics of the reference product (placebo) are given below:

Substance: Placebo (citrate buffer, pH 6.5)

Pharmaceutical formulation: solution for infusion

Source: BI Pharma GmbH & Co. KG, Germany

Unit strength: not applicable

Posology: 1-0-0

Route of administration: IV infusion

Duration of use: Single dose (20 mg/kg b.w.)

Multiple dose (4 single IV administrations one week apart)

#### 4.1.2 Method of assigning subjects to treatment groups

Prior to the screening visit, subjects will be contacted in writing and informed about the planned visit dates. The subjects willing to participate will be recruited to dose groups according to their temporal availability. As soon as enough subjects have been allocated to 1 of the 11 dose cohorts (2 cohorts per dose group in the MRD part, 3 cohorts in the SRD part), the following subjects will be allocated to one of the other dose cohorts. Therefore, the allocation of subjects to dose cohorts is not influenced by trial personnel, but only by the subjects' temporal availability. As the study includes healthy subjects from a homogenous population, relevant imbalances between the dose groups are not expected.

The randomisation list with study subject numbers and allocated treatments (SRD part) and the list of subject and medication numbers (MRD part) will be provided to the trial site in advance. The allocation of subjects to study subject numbers will be performed prior to the first administration of trial medication. For this purpose, the subjects will be allocated to a study subject number by drawing lots. Once a subject number has been assigned, it cannot be reassigned to any other subject.

The randomisation procedure is described in [Section 7.5](#).

#### 4.1.3 Selection of doses in the trial

The doses selected for this trial cover the subtherapeutic as well as the estimated therapeutic range and include a safety margin (see [Section 1.2](#)).

#### 4.1.4 Drug assignment and administration of doses for each subject

The treatments to be evaluated are outlined in [Table 4.1.4: 1](#) below. The dose volume for placebo corresponds to the dose volume of the respective dose level. For further details concerning timing see [Flow Chart](#). Start and time of the infusion will be recorded.

Detailed instructions for the dilution of the trial product, the preparation of the infusion solution, the volume to be administered and the infusion rate is provided in [Appendix 10.2](#). In all subjects the infusion solution will be intravenously administered over 30 minutes for dose group 3 mg/kg b.w. multiple dose and 6 mg/kg b.w. multiple dose and over 60 minutes for dose group 10 mg/kg b.w. multiple dose and 20 mg/kg b.w. single dose approximately between 8.00 h and 10.30 h of the respective study day. Multiple doses of 20 mg/kg b.w. will be administered over 90 minutes between 8.00 h and 12.00 h of the respective study day.

In case of safety concerns, e.g. due to infusion reactions, it is in the discretion of the investigator or his/her designee to adapt the infusion scheme, including but not limited slowing down the infusion rate, stopping of the infusion and provided no further safety concern exist restarting at a slower rate. Further based on █ medical judgment he/she will provide medications such as steroids, etc. as needed.

For administration of the infusion, an intravenous indwelling catheter is placed into an arm vein of the subject and will be kept patent with a saline infusion. A second indwelling catheter used for collection of blood samples will be placed on the contralateral arm.

The administration of the trial medication on all study days will be done under supervision of the investigating physician or a designee. The so-called four-eye principle (two-person rule)

should be applied for administration of trial medication and – if applicable – its preparation (e.g. reconstitution), if correct dosage cannot be ensured otherwise. For the purpose of drug accountability, the infusion set will be weighed before and after drug administration.

Table 4.1.4: 1 Preparation of infusion solution containing active drug

Dose group	Final dose of BI 655130 [mg/kg]	Concentration of Application solution in infusion bag	Infusion volume [mL]*/ Total dose [mg]
1	3	20 mg/mL	9 mL → 180 mg
2	6	20 mg/mL	18 mL → 360 mg
3	10	20 mg/mL	30 mL → 600 mg
4	20	20 mg/mL	60 mL → 1200 mg
5	20	20 mg/mL	60 mL → 1200 mg

\*Infusion volume for a body weight of 60 kg.

Water is allowed except for 1 hour before start of infusion and 1.5 h after end of infusion. On Day 1 for all dose groups and in addition Day 8, Day 15 and Day 22 for subjects receiving repeated doses (dose group 1 to 3), from 2 hours post-dose, liquid intake is restricted at additional 3000 mL until the morning of Day 2. Standardised meals will be served as outlined in the [Flow Chart](#). Subjects will be kept under close medical surveillance until 48 h following drug administration. Thereafter subjects will be discharged from the CPU and further assessments will be conducted in an ambulatory fashion. For restrictions with regard to diet see also [Section 4.2.2.2](#).

